- Group A Prevention cohort: To estimate the proportion of participants with no evidence of SARS-CoV-2 infection at or before day 28
For the purpose of the study endpoint, SARS-CoV-2 infection is defined as any of the following outcomes:
 - SARS-CoV-2 detected in upper respiratory samples at any of day 7, day 14 or day 21; or
 - New finding of serum antibodies (IgA or IgG) against the SARS-CoV-2 spike protein according to validated specifications and performance characteristics before or on day 28.
- Group B. Treatment cohort: Proportion of participants with resolved SARS-CoV-2 infection at Day 14 defined as non-detection of SARS-CoV-2 RNA in two respiratory samples before or on day 14

SECONDARY OUTCOMES

Group A Prevention cohort

- Time to onset of signs and symptoms consistent with COVID -19 (Symptoms: Cough, sore throat, generalized body aches and shortness of breath; Signs Fever >100.4 F, RR >25, SpO2 <95% on room air)
- Hospitalization
- Proportion with treatment-emergent adverse events

Group B Treatment cohort

- Time to onset of signs and symptoms consistent with COVID -19 (Symptoms: Cough, sore throat, generalized body aches and shortness of breath; Signs Fever >100.4 F, Respiratory rate >25, SpO2 <95% on room air)

- Incidence of progressive clinical disease at or before 14 days after enrollment assessed by SpO₂ (determined by home pulse oximetry, when available).
- Hospitalization
- Time to clinical resolution of signs and symptoms consistent with COVID-19 (Among those that develop symptoms)
- Proportion with treatment emergent adverse events

EXPLORATORY OUTCOMES

- Relationship of outcomes with genetic polymorphism related to interleukin-28b
- Compare the rates, levels and duration of SARS-CoV-2 RNA in upper respiratory samples using RT-PCR

[figure not shown]
KEY INCLUSION

- Willing and able to provide written informed consent
- Peripheral capillary oxygen saturation (SpO₂) \geq 95% on room air at screening
- Age \geq 18 years to \leq 80 years

KEY EXCLUSION

- Hospitalized or impending hospitalization at the time of screening
- Symptoms of cough, fever or shortness of breath within 72 hours
- Prior or current treatment with other experimental or approved agents targeting SARS-CoV-2 or SARS-CoV-1
- Positive pregnancy test
- Active autoimmune disease or sarcoidosis (with the exception of controlled thyroid disease)
- Active decompensated liver disease (ascites, encephalopathy)
- Active congestive heart failure

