3.1.2 Treatment Cohort

Peginterferon lambda-1a will result in a higher proportion of participants with resolved SARS-CoV-2 infection at Day 14.

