12.2 Group B Treatment cohort primary endpoint

- Resolution of SARS-CoV-2 defined as non-detection of SARS-CoV-2 RNA in two

respiratory samples by or on day 14

13. Statistical Considerations

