13.1 Sample Size and Power Considerations

The planned sample size for the trial is 164 participants enrolled and randomized in a 1:1 ratio to lambda interferon-1a versus placebo injection. This sample size is based on the expectation that approximately 32.5% of participants who are enrolled have evidence of SARS-CoV-2 at study entry (an intermediate value consistent with the 25 – 40% infection range that we expect for the study outcome in the placebo group), thus around 110 will be will have no evidence of SARS-CoV-2 infection (Prevention Cohort) at enrollment and around 54 participants will have evidence of SARS-CoV-2 infection (Treatment Cohort). The Treatment Cohort represents an exploratory pilot study to provide estimates of antiviral efficacy for early COVID-19. Power estimates for the study are based on the Prevention Cohort and incorporate the following assumptions (multiple credible scenarios are presented):

The primary analysis for the efficacy/prevention of infection with SARS-CoV-2 in the Lambda interferon-1a and the placebo groups using proportional odds model and a two-sided Type I error rate (α) of 0.05. Since participants in both the Prevention and Treatment Cohorts will be dosed after entry, we anticipate that few, if any participants will not start treatment and be excluded from the primary analysis. Further, given the nature of COVID-19, we anticipate low rates of loss to follow-up before the primary endpoint (Day 14). We expect the incidence of new COVID-19 in the placebo group to be between 25% to 40%, thus we will perform calculation for these edge-case scenarios. In addition, we will be offering enrollment to all adults in a household (~2 per household), our analysis sample will be clustered-correlated by household. However, there is no preliminary or published data to model within-cluster correlation. Thus we are modeling scenarios where the effective sample size is as high as 110 individuals, or as low as the number of households of 55. In all scenarios, we are expecting that the cumulative infection fraction for the lambda interferon will be 5%.

Cumulative Infection Percentage in Placebo	Effective sample size	
	N= 110 individuals	N = 55 family clusters
25%	80.1%	36.1%
40%	99.6%	84.0%

We note that we have 80% or greater power (and Type II error rate beta of 0.2 or smaller) in a large range of scenarios.

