13.2 Statistical Analysis

13.2.1 Analyses will include all randomized participants Our primary analysis for both the prevention and treatment cohorts (outcomes of non-infection and resolution, respectively) will be mixed model logistic regression correcting for within-household correlation as a random effect. In addition to the placebo cumulative infectivity and odds ratios, we will express the overall

cumulative incidence of infection and the difference between lambda interferon vs. placebo using nonlinear combination (i.e., inverse logit of the placebo and active treatment groups and the difference of these after the inverse logit transformation). Statistical inference will use a two-sided Type 1 error rate of 0.05 and 95% confidence intervals.

For the exploratory treatment cohort, we will similarly examine clearance of infection.

In addition, we will perform survival analysis for time to infection in the prevention cohort and time to infection clearance in the treatment cohort, modeling within cluster correlation of hazard as a random effect (frailty).

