14.4 Study stopping rules

We will pause enrollment after 50% of participants have reached study end point and wait until the DSMB has completed their planned review prior to resuming enrollment

We will use O'Brien and Fleming limits as the stopping rule based on efficacy (threshold p-values of 0.0054 at mid-planned sample and 0.0492 for the final analysis). For the futility stopping rule, we will use a conditional power of < 10% at the time of mid-sample accrual, assuming that the remaining sample will have the same treatment success as the sample accrued so far.

15. Protection of Human Subjects

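### Group B viral clearance is labelled both primary and exploratory, and the interim rules do not say which cohort they apply to

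*Combined protocol and SAP*

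**What the plan says.** **Group B as primary.** The synopsis lists under its primary outcomes "Group B. Treatment cohort: Proportion of participants with resolved SARS-CoV-2 infection at Day 14". Section 3.1.2 gives a directional hypothesis: "Peginterferon lambda-1a will result in a higher proportion of participants with resolved SARS-CoV-2 infection at Day 14". Section 3.2.2 places Group B resolution under the primary objective, worded as estimation. Section 12.2 is headed "Group B Treatment cohort primary endpoint". Section 13.2.1 begins "Our primary analysis for both the prevention and treatment cohorts (outcomes of non-infection and resolution, respectively", and its paragraph ends: "Statistical inference will use a two-sided Type 1 error rate of 0.05 and 95% confidence intervals".

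**Group B as exploratory.** The synopsis entry on sample size calls it an exploratory cohort. Section 13.1 says: "The Treatment Cohort represents an exploratory pilot study to provide estimates of antiviral efficacy for early COVID-19". A later line of 13.2.1 again calls the treatment cohort exploratory.

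**Ranking of the cohorts.** Section 5 identifies Group A as the primary study population and introduces Group B as an added opportunity. Section 13.1 bases power on Group A only, and ties its 0.05 to prevention of infection: "using proportional odds model and a two-sided Type I error rate (α) of 0.05".

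**Interim look.** Section 14.1 schedules the DSMB review once half the planned participants have reached the primary endpoint. Section 14.4 says "We will use O'Brien and Fleming limits as the stopping rule based on efficacy", gives p-value thresholds of 0.0054 and 0.0492, and adds a futility rule at conditional power below 10%. Neither section names a cohort or an endpoint.

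**The concern.** The two labels lead to different reports of the same result. Because the text supports both, the status of Group B could be settled after the data are seen: a favourable clearance result could be presented as a primary success, and an unfavourable one as a pilot. Prespecification is meant to rule this out. The conflict sits inside a single subsection, 13.2.1, so it cannot be put down to a simplified synopsis.

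The interim rules turn the ambiguity into a practical problem. Group A's endpoint runs to day 28 and Group B's to day 14. Section 13.1, in its remark on loss to follow-up, places the primary endpoint at day 14, which is Group B's timing. From this text a DSMB could not tell whose endpoints are counted towards the 50% trigger, whose p-value is compared with 0.0054, or whose conditional power decides futility.

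**Working it through.** **1. The plan's own figures.** The inputs from 13.1 are 25% or 40% infected on placebo, 5% on Lambda, 1:1 allocation, an effective sample of 110 or 55, and two-sided alpha 0.05. Exact enumeration of Fisher's test reproduces all four cells of the power table:

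| Placebo infection | 55 per arm | 27 per arm |
|---|---|---|
| 25% | 80.1% | 36.1% |
| 40% | 99.6% | 84.0% |

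The power calculation therefore spends the whole 0.05 on the Group A comparison and leaves nothing for a second primary test.

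**2. Cohort sizes.** Group A: 164 × 0.675 = 110.7. Group B: 164 × 0.325 = 53.3. These agree with the plan's 110 and 54.

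**3. Group B exploratory.** There is one primary test, in Group A. Its error is 5% two-sided, or 2.5% in favour of Lambda, whatever happens in Group B.

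**4. Group B a second primary test at 0.05, with either cohort counting as success.** The cohorts contain different participants, so independence is the natural starting assumption.
- Any significant result: 1 − 0.95² = 9.75%.
- Results favouring Lambda only: 1 − 0.975² = 4.94%, against 2.5% for one test.

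Households with members in both cohorts could correlate the two tests. With assumed correlations of 0.1, 0.3 and 0.5, the two-sided figure becomes 9.7%, 9.5% and 9.1%. The exact value is therefore not sensitive to this.

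**5. The 14.4 thresholds.** Assume one look at half information, with correlation √0.5 between the looks. The critical values are z = 2.782 and 1.967.
- One cohort: 5.13% two-sided overall, 2.56% in favour of Lambda.
- Thresholds on Group A and a single 0.05 test on Group B: 1 − (1 − 0.0513) × 0.95 = 9.87%.
- Thresholds on both cohorts: 1 − (1 − 0.0513)² = 10.0% two-sided. In favour of Lambda: 1 − (1 − 0.02565)² = 5.06%.

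The step from 9.75% to 10.0% comes from the printed thresholds, which slightly overspend 0.05 on their own. It does not come from the status of Group B.

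**6. False crossing at the interim look.** If both cohorts are compared with 0.0054, the two-sided chance goes from 0.54% to 1 − (1 − 0.0054)² = 1.08%. In favour of Lambda it goes from 0.27% to 1 − (1 − 0.0027)² = 0.54%.

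**7. The trigger.** Half of all enrolled is 82; half of Group A is 55. Under the assumed 32.5% positivity the two counts agree on average (82 × 0.675 = 55.4). They do not mature together, because a Group B participant reaches the endpoint by day 14 and a Group A participant only at day 28.

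**The case against.** The strongest reply is that the plan does rank the cohorts. Section 5 names Group A as the primary study population, the synopsis and 13.1 size the trial on it, and the heading of 12.2 can be read as the main endpoint within Group B. On that reading no error inflation comes from Group B. This stands as an account of what was probably intended. It does not remove the directional hypothesis in 3.1.2, the entry under primary outcomes or the opening of 13.2.1, and it does not supply a testing order.

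A reader might infer that the trial's false-positive rate is about 10% instead of a promised 5%. The documents do not support that, for three reasons:
- The 0.05 is stated per analysis, and no family-wise rate is promised.
- Conflicting labels do not inflate error by themselves. Inflation needs Group B to be co-primary and either cohort to suffice, and no section says that either suffices.
- The figure of about 10% counts significant results in both directions. Both hypotheses are directional, so the false successes they describe go from 2.5% to about 4.9%. The doubling is the same; the level is not.

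It can also be said that joint error control over separate populations with separate hypotheses is a matter of convention. That is fair, and it is why the plan needs to define its trial-level claim.

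An efficacy stop driven by Group B is a possibility that the wording leaves open, not something the plan provides for; under 14.1 the DSMB also reviews safety, progress and conduct.

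Low power in Group B adds little. With Fisher's test at 27 per arm, power is 23% for 50% vs 70% clearance, 55% for 50% vs 80%, 80% for 40% vs 80% and 87% for 50% vs 90%. All these rates are assumed, Fisher's test is not the planned mixed model, and power has no bearing on false positives.

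**Conclusion.** The contradiction is real and should be resolved before any unblinded comparison. Group B resolution is both a primary outcome with a directional hypothesis and 0.05 inference, and an exploratory pilot. Sections 14.1 and 14.4 leave open which cohort governs the interim decision.

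The size is conditional. If Group B is a second primary test and either cohort counts as success, the chance of at least one false-positive primary result is up to about 9.75% two-sided, or about 4.9% against 2.5% in favour of Lambda. This assumes independent tests at their nominal level and no adjustment. If Group B is exploratory, the Group A error rate is unaffected by it. The plan does not say which case applies, so neither figure can be given as the trial's error rate. The interim gap stands whatever view is taken on multiplicity.

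**What to change.** 1. In the synopsis, 3.1.2, 3.2.2, 12.2 and 13.2.1, state that Group A non-infection is the sole primary (confirmatory) endpoint. This follows the synopsis entry on sample size, section 5 and 13.1.
2. Relabel Group B resolution as the main exploratory endpoint, reported as an estimate with a 95% confidence interval and no confirmatory claim.
3. In 14.1 and 14.4, state that the 50% trigger, the efficacy thresholds and the conditional power use the Group A primary endpoint only. Reconcile the day 14 reference in 13.1 with that endpoint.
4. If the sponsor prefers to keep Group B as primary, add a fixed testing order with Group A first, or an alpha split. At 0.025 each, the two-sided total is 1 − 0.975² = 4.94%, but the 13.1 power table would then need recalculating.

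Items 1 to 3 change wording only and leave the sample size and data collection as they are. The cost is that a Group B p-value below 0.05 could not be presented as a primary success, which agrees with how 13.1 already describes that cohort.

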3.3.2.4 To estimate the time to resolution of SARS CoV-2 infection

3.4 Exploratory objectives

3.4.1 To assess the relationship of primary outcomes to genetic polymorphism in the region of the gene interleukin-28B

3.4.2 To compare the rates, levels and duration of SARS-CoV-2 RNA in respiratory samples using RT-PCR

4 Background

Severe acute respiratory syndrome coronavirus 2 (SARS-CoV-2) has emerged as a major cause of upper and lower respiratory tract infection which progresses to severe pneumonia in approximately 15% of infected persons with potential progression to adult respiratory distress syndrome (ARDS) and, death in 1 to 3% of persons infected [1]. However, SARS-CoV-2 infection also manifests with relatively mild respiratory tract infection symptoms such as cough, sore throat and fever, or with no symptoms (asymptomatic infection) [2]. Collectively, respiratory illness due to SARS-CoV-2 is referred to as Coronavirus Disease 2019 (COVID-19). Antiviral treatments are urgently needed to prevent transmission and treat persons with early infection to prevent clinical progression to severe pneumonia and ARDS. While studies are underway, there are no approved treatments for persons with COVID-19 [3]. Similarly, early antiviral treatment may limit the transmission of SARS-CoV-2. While several host risk factors, like age and chronic comorbid diseases, have been associated with severe COVID-19, transmission of the virus from persons with minimal or no symptoms is estimated to account for as much as 78% of infections in the pandemic [4]. While studies of prophylactic vaccination are underway, medications to prevent person-to-person transmission are urgently needed.

In humans, the innate immune response to viral infections involves type I and type III interferons. Interferon alpha is a type I interferon that binds to broadly-expressed cell surface co-receptors which activates the JAK-STAT signal transduction pathway and upregulates numerous interferon-stimulated genes. Interferon lambda is a Type III interferon which binds to a receptor complex which is distinct from those used by type I interferons but appears to activate the same signaling cascade and stimulates cell-mediated immune responses that are critical for the development of host protection during viral infections [5].

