8.9. Randomization

Randomization will take place on day 0 after screening activities have been performed and the Investigator or designee has determined that the participant is eligible. Day 0 laboratory tests including blood SARS-CoV-2 RT-PCR results are not part of the eligibility criteria and participants will be randomized without this information. Randomization will be built into the study REDCap database. It will not be known at entry/screening whether participants are part of Group A or Group B since their COVID-19 infection status will not be known until entry/screening specimens are processed. All participants will be randomized in a 1:1 ratio to receive Lambda/Lambda (Arm 1) or Placebo/Placebo (Arm 2). Participants who are not eligible for enrollment into Step 2 (will be removed from protocol therapy Single dose of Lambda or placebo) respectively.

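### The Group B clearance model leaves out the Day 0 SARS-CoV-2 RNA level, the baseline of its own outcome; adjusting for it is a low-cost gain in precision for an exploratory cohort

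*Combined protocol and SAP*

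**What the plan says.** Section 13.2.1 sets one primary model for both cohorts: it "will be mixed model logistic regression correcting for within-household correlation as a random effect". Apart from treatment arm, no fixed covariate is named there, in the frailty survival models of 13.2.1 and 13.2.2, or in the missing-data section 13.2.3. The same section adds that "Statistical inference will use a two-sided Type 1 error rate of 0.05 and 95% confidence intervals".

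The Group B endpoint (12.2) is binary: SARS-CoV-2 RNA not detected in two respiratory samples by Day 14.

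Section 8.9 randomizes 1:1, names no stratification factor, and says of the Day 0 laboratory results that "participants will be randomized without this information".

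The Step 1 schedule (7.1) takes an upper respiratory specimen from everyone on Day 0, and its RT-PCR result assigns people to Group A or Group B (Synopsis, Population and Regimen). Exploratory objective 3.4.2 is "To compare the rates, levels and duration of SARS-CoV-2 RNA in respiratory samples using RT-PCR".

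On size and status, 13.1 expects that "approximately 32.5% of participants who are enrolled have evidence of SARS-CoV-2 at study entry", which gives a Group B of around 54. It adds: "The Treatment Cohort represents an exploratory pilot study to provide estimates of antiviral efficacy for early COVID-19". No power, clearance rate or effect size is given for Group B.

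**The concern.** Whether RNA has become undetectable by a fixed day plausibly depends on how much was there at the start. The baseline value of an outcome is usually the first covariate to consider, and here the model leaves it out. Because arms are assigned before PCR status is known, the design cannot balance starting RNA within Group B. That leaves adjustment in the analysis as the available remedy.

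At stake is the quality of the pilot estimate. If the level is prognostic, an unadjusted comparison of about 27 per arm is less precise than it could be. In a sample that happens to be imbalanced, the observed clearance difference also moves with the imbalance.

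**Working it through.** **The plan's own figures.** 164 × 0.325 = 53.3 and 164 × 0.675 = 110.7, close to the stated 54 and 110. That gives about 27 per arm in Group B. The only power table (13.1) concerns the Prevention Cohort. The two-sided Fisher exact test with 55 and 27 per arm reproduces all four cells (80.1%, 36.1%, 99.6% and 84.0%). Nothing comparable exists for Group B.

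**Inputs.** From the documents: 27 per arm, 1:1 allocation, two-sided alpha 0.05, binary clearance. Assumed, because the documents give no figures: the clearance rates, the strength of the RNA effect, and a log10 RNA SD of 1.5 to 2.

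**Power.** Model: logit P(clear) = a(arm) − ln(OR) × z. Here z is the standardised Day 0 RNA level, and OR is the factor by which the odds of clearance fall per SD of RNA. The intercepts are solved so that marginal clearance stays at the stated rates whatever the OR. Each cell is 3,000 simulated trials. The arm effect is tested by a 1-df likelihood-ratio test, without and then with z. The household effect is left out. Entries are unadjusted → adjusted, in percent.

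| Clearance, placebo vs lambda | OR 1 | OR 2 | OR 3 | OR 5 |
|---|---|---|---|---|
| 50 vs 80 | 67.4 → 66.4 (−1.0) | 66.3 → 70.4 (+4.1) | 68.1 → 75.4 (+7.3) | 68.5 → 81.9 (+13.4) |
| 40 vs 75 | 75.9 → 76.0 (+0.1) | 75.3 → 80.0 (+4.7) | 75.3 → 83.6 (+8.3) | 75.9 → 89.4 (+13.5) |
| 60 vs 90 | 76.5 → 75.6 (−0.9) | 78.2 → 81.0 (+2.8) | 78.2 → 82.9 (+4.7) | 77.9 → 88.5 (+10.6) |
| 50 vs 50 (type I error) | 4.5 → 5.2 | 4.4 → 5.4 | 4.1 → 5.2 | 4.2 → 5.0 |

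Repeat runs at 50% vs 80% gave gains of 1 to 3 points at OR 1.8, 5 to 7 at 2.7, 8 to 9 at 3.3, and 12 to 14 at 5. In repeat runs the adjusted type I error lay mostly between 5% and 6%, with a highest value of 6.6%. The adjusted test is therefore slightly liberal at this size, and part of each gain reflects that.

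**Chance imbalance.** The SD of the between-arm difference in mean RNA is SD × √(2/27).
- SD 1.5: 0.408 log10, so P(|difference| > 0.5 log10) = 22%.
- SD 2: 0.544 log10, so P(|difference| > 0.5 log10) = 36%.
- In SD units the standard error is 0.27. An imbalance of at least 0.3 SD has a 27% chance, and of at least 0.5 SD a 6.6% chance.

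**What an imbalance does.** With no drug effect and 50% clearance, a 0.3 SD imbalance moves the observed difference by 4.7, 6.6 or 8.2 points at OR 2, 3 or 5. A 0.5 SD imbalance moves it by 7.8, 11.0 or 13.7 points. A 0.5 log10 imbalance is 0.5/2 = 0.25 to 0.5/1.5 = 0.33 SD, which corresponds to about 5 to 8 points. The standard error of the unadjusted difference is √(2 × 0.5 × 0.5/27) = 13.6 points, so 5 to 8 points is about 0.4 to 0.6 of a standard error.

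**The case against.** The strongest reply is that nothing here is broken. The unadjusted test holds its type I error (4.1% to 4.5% above), and the planned 95% interval already allows for random imbalance. Group B is labelled an exploratory pilot with no power claim, so no stated design property fails. All of that stands and limits the weight of the point. It does not remove it: 13.2.1 still gives Group B a primary model with formal inference, and the purpose of the cohort is an estimate whose precision can be improved.

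Two further objections also stand in part. No section shows that Day 0 RNA predicts clearance. If it does not, the gain is nil and up to about 1 power point is lost. Nor do the documents say that the Day 0 RT-PCR is quantified; that is inferred from the planned comparison of levels in 3.4.2. Section 8.11 lets specimen type depend on collection site and swab supply, although the Synopsis describes the entry sample as nasopharyngeal. A noisy covariate would gain less.

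A reader might go further and infer that imbalance is likely, or that randomizing before the PCR result biases the comparison. The figures do not support the first: even under the assumed SDs, an imbalance above 0.5 log10 is absent in 64% to 78% of trials. The second is wrong, because allocation is still random within Group B.

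**Conclusion.** The omission is real, and no other section supplies a covariate or a stratification factor. It is a matter of precision and of a possibly misleading individual sample, not of validity or design bias.

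Under the assumptions above, adjustment changes Group B power by about -1 to 0 points if RNA is not prognostic. It adds about 2 to 5 points at an odds ratio near 2 per SD, 5 to 9 near 3, and 11 to 14 at 5. These sizes depend on assumed clearance rates and prognostic strength, leave out the household effect, and include some contribution from the slightly liberal adjusted test. The 22% to 36% chance of an imbalance above 0.5 log10 depends on the assumed SD of 1.5 to 2.

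This is a low-cost improvement for an exploratory cohort. The Prevention Cohort, PCR-negative at Day 0, is unaffected.

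**What to change.** In 13.2.1, pre-specify Day 0 log10 SARS-CoV-2 RNA (or Day 0 Ct value) as a linear covariate in the Group B clearance model and in the Group B time-to-clearance frailty model, keeping the household random effect. Report the clearance difference standardised over the covariate, with the unadjusted result alongside. The standardised difference suits the inverse-logit difference that 13.2.1 already plans, whereas the adjusted odds ratio is conditional on the covariate. State that the Day 0 specimen is quantified, and make this change before any unblinded analysis.

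The cost is a few sentences in the plan, with no added participants or visits if the Day 0 result is quantified. The downside is at most about 1 power point if the level is not prognostic, slightly liberal small-sample tests, and some noise from varying swab type.

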8.15.3 Pregnancy monitoring and reporting

All participants of childbearing potential must follow the contraception requirements listed in section 6.1.1.6 from Day 0 to Day 84. A pregnancy test will be administered at screening to confirm that pregnant women are not enrolled in this study. Female participants will be asked to confirm ongoing use of required contraception and to report pregnancy through Day 84. Male participants will be asked to confirm ongoing use of required contraception and to report pregnancy of female partners through Day 84.

If a female participant or the female partner of a male participant becomes pregnant while on this study, the investigator/ designee will request to follow the pregnancy to its

outcome. Pregnant partners of male participants will not be required to provide records for themselves or their fetus/child but may do so under a separate HIPAA medical records request form if they choose. Pregnant female participants will be required to provide this information for themselves and the fetus/child unless they withdraw consent from this study.

Pregnancy is not reported as an adverse event, however, it will be reported to Eiger Biopharmaceuticals and the FDA as per voluntary reporting requirements.

8.16 Assessment of exposure to SARS-CoV-2 through household survey.

Dose of exposure to SARS-CoV-2 will be assessed through assessment of household size, household relationships COVID -19 exposure and social distancing measures employed within and outside the home assessed at baseline and day 14. If unable to conduct household survey at Day 0, the survey may be conducted by phone anytime before Day 14 evaluation. We will utilize validated survey items from the NIH Public Health Emergency and Disaster Research Response (DR2) repository (<https://dr2.nlm.nih.gov/>).

Surveys are adapted from the COVID-19 Household Environment Scale (https://www.phenxtoolkit.org/toolkit_content/PDF/Behar_Zusman_CHES_ENG.pdf) and the WHO Household transmission investigation protocol for 2019-novel coronavirus (COVID-19) infection.

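### The Group A primary model adjusts for no baseline exposure variable: a small efficiency loss, about 0 to 3 points of power under the plan's own scenarios, and not a validity problem

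*Combined protocol and SAP*

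**What the plan says.** Section 13.2.1 states that the primary analysis for both cohorts "will be mixed model logistic regression correcting for within-household correlation as a random effect", and that "Statistical inference will use a two-sided Type 1 error rate of 0.05 and 95% confidence intervals". Arm and household are the only terms implied. Section 13.1 describes the primary analysis as "using proportional odds model and a two-sided Type I error rate (α) of 0.05". For a binary outcome that is a logistic model, and it too names no covariate. Sections 13.2.2 and 13.2.3 add none.

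Section 8.16 says: "Dose of exposure to SARS-CoV-2 will be assessed through assessment of household size, household relationships COVID -19 exposure and social distancing measures", inside and outside the home, at baseline and day 14. If the survey cannot be done at Day 0, "the survey may be conducted by phone anytime before Day 14 evaluation". Footnote a to table 7.1 repeats this, and table 7.2 gives the Day 14 visit a window of ±4 days. No section assigns the survey to any analysis. Criterion 6.1.1.4 requires the index case to have been diagnosed in the preceding 7 days, and the Step 1 criteria must be documented at Day 0.

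Section 13.1 plans about 110 Group A participants, allocated 1:1, with placebo infection between 25% and 40%. In every scenario "we are expecting that the cumulative infection fraction for the lambda interferon will be 5" per cent.

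**The concern.** Household exposure is the risk on which this trial enrols, so a baseline measure of it is a natural candidate to predict infection. Adjusting for a predictive baseline variable raises the power of the treatment test, tightens the risk difference, and accounts for chance imbalance between two arms of about 55. With few infections expected, such imbalance is possible. The information is collected anyway, so leaving it out forgoes precision at no saving.

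The timing of the survey bears on which variable could be used. A nominal Day 0 survey may be answered after dosing, after symptoms, or after the Day 7 swab, which counts toward the Group A endpoint (12.1). An answer given then may partly reflect the outcome.

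**Working it through.** **1. The plan's own power figures.** Inputs from 13.1: two-sided 0.05, lambda 5%, placebo 25% or 40%, effective N of 110 (55 per arm) or 55 (27 per arm, rounding down). Enumerating two binomials with a two-sided Fisher's exact test gives:

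| Placebo | N = 110, plan / recomputed | N = 55, plan / recomputed |
|---|---|---|
| 25% | 80.1% / 80.1% | 36.1% / 36.1% |
| 40% | 99.6% / 99.6% | 84.0% / 84.0% |

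All four cells match, so the stated power corresponds to an unadjusted two-proportion test. The simulations below use likelihood-ratio tests, which are less conservative than Fisher's test. Their unadjusted power is therefore near 88% rather than 80.1%, and only the difference between unadjusted and adjusted matters here.

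**2. Expected infections at 55 per arm.**
- 25% vs 5%: 55 × 0.25 + 55 × 0.05 = 13.75 + 2.75 = 16.5.
- 40% vs 5%: 55 × 0.40 + 55 × 0.05 = 22 + 2.75 = 24.75.

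These counts support one extra term, not a set of them.

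**3. Gain within the plan's scenarios.** Assumptions: 55 households of 2 (except where contacts are independent), individual randomisation, one standard-normal exposure score, intercepts solved so that marginal risks match the stated percentages. The odds ratio per SD is assumed throughout. Results at 25% vs 5%:

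| Setting | OR per SD | Unadjusted | Adjusted | Change |
|---|---|---|---|---|
| Household-level score, household SD 0.5, fixed-effect logistic, 3,000 trials | 1 | 88.5% | 88.0% | −0.5 |
| same | 2 | 89.0% | 89.9% | +0.9 |
| same | 3 | 87.0% | 89.9% | +2.9 |
| Repeat of that design, 3,000 trials | 1 | 89.5% | 89.1% | −0.4 |
| same | 2 | 89.8% | 90.6% | +0.8 |
| same | 3 | 88.4% | 90.6% | +2.2 |
| Household random effect in both models, SD 1.0, score half shared, 500 trials | 1.5 | 89.0% | 89.0% | 0.0 |
| same | 2 | 88.6% | 89.0% | +0.4 |
| same | 3 | 90.6% | 93.6% | +3.0 |
| same, score fully shared within household | 3 | 89.8% | 91.8% | +2.0 |
| same, score not shared | 3 | 87.2% | 90.8% | +3.6 |
| Independent contacts, individual-level score, 4,000 trials | 3 | about 88% | 91.8% | about +3.8 |

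Monte Carlo SE is at most 0.9 points with 3,000 trials, and √(0.9 × 0.1 / 500) = 1.3 points per power estimate with 500. A further run of the first design (1,504 trials per cell, OR 3) gave +2.8 points with the plan's random-intercept model and +3.3 with fixed effects. The values above 3 with a household random effect or independent contacts need a score that varies between members of a household. Time since index diagnosis and household size are largely shared, so the household-level rows are the relevant ones.

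At 40% vs 5%, OR 3, the random-intercept model gave 99.8% unadjusted and 99.9% adjusted.

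In the random-effect runs without reporting error, the variance of the standardised risk difference fell by about 1% to 9%. The gain shows up there and in the test. The standard error of the conditional odds ratio does not shrink.

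**4. Outside the plan's scenarios.** At OR 3, 25% vs 10% moved from 57.2% to 62.1% (+4.9), and 40% vs 15% from 85.7% to 91.2% (+5.5; +4.7 with the random-intercept model). Both need a smaller lambda effect than 13.1 assumes.

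**5. Type I error.** It was 5.2% to 5.8% with or without the term in the first design, and 5.3% unadjusted vs 5.0% adjusted in the repeat.

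**6. Using late survey answers.** Random-effect model, 25% vs 5%, OR 2, with the reported score shifted upward in infected contacts:
- Shift 0.5 SD: mean risk difference −0.200 unadjusted, −0.184 adjusted; power 87.6% to 86.8%.
- Shift 1 SD: −0.199 to −0.157; power 90.0% to 80.8%.

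A covariate contaminated in this way can lose about 9 points, more than a clean one gains.

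**The case against.** The strongest reply is that nothing is broken. Randomisation makes the unadjusted comparison valid, no section promises an exposure-adjusted analysis, and the household random effect already models shared variation. The prognostic strength is unknown, survey items are self-reported, and time since diagnosis spans only 0 to 7 days. All of this stands, and it is why the point is one of efficiency and its size is small.

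A reader might infer more in three ways, none of which the documents support:
- **That omitting exposure biases the result.** It does not; it only leaves some precision unused.
- **That about 5 points of power are being lost.** Gains of that size appeared at lambda risks of 10% and 15%, whereas 13.1 fixes lambda at 5% throughout.
- **That the late survey window damages the primary analysis.** No analysis in section 13 uses the survey, so its timing harms nothing now planned. Late completion is a fallback of unknown frequency, and the documents do not say when participants learn their results. The Day 0 swab cannot separate Group A members in any case, since all are RT-PCR negative by definition. The window matters only for choosing a covariate.

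**Conclusion.** The point holds as a minor, optional improvement. The term would earn its place only if exposure predicts infection: at an assumed odds ratio of 2 per SD the household runs gained less than 1 point, and at 3 about 2 to 3. The figures also rest on individual randomisation, about two contacts per household and a score measured without error; a noisier score would gain less. Since the downside is smaller than the plausible gain, adding one well-chosen term is reasonable. Leaving it out would not undermine the trial's conclusion.

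**What to change.** In 13.2.1, add exactly one pre-specified covariate to the Group A primary model, with its value fixed before dosing. Days from index diagnosis to Day 0 is preferable, because 6.1.1.4 already requires it to be established at entry. Household size as of Day 0 is an alternative.

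- Obtain the inverse-logit risks and their difference, which 13.2.1 already plans, by averaging over the covariate's distribution in Group A.
- Keep the unadjusted mixed model as a supportive analysis.
- Exclude behavioural items, such as distancing, that were answered after dosing. Requiring answers before the Day 7 swab result would not be enough: symptoms are screened on Days 1–6 (7.1), and symptomatic contacts are sent for testing (8.1.1, 8.11).
- Replace a missing covariate value by a simple rule blind to arm and outcome, such as the overall mean. Dropping those participants would conflict with the commitment in 13.2.1 to analyse everyone randomised.

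The cost is a few sentences of analysis text and one extra parameter, with no change to sample size, visits or treatment.
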